8.3 Randomization

If all inclusion and exclusion criteria are met, the patient will be contacted to agree on a time for study drug administration. Apotek Produktion & Laboratorier, APL, is then contacted for randomization and ordering of study drug.

The study drug is delivered to the centers in ready-made infusion bags with refrigerated transport and temperature log by World Courier. The study drug is stored after delivery from APL in a refrigerator (+ 2-8 °C) until administration.

In addition to the study drug, study participants may receive other immunosuppressive treatment according to what is listed in the protocol under section 10.7, Permitted / non-permitted treatment at different times.

Protocoll nr: 2015-00887 Date: 2021-04-26 Version 7.0 (ENG)

8.4 Study drug administration, baseline (V.0)

Study drug administration is carried out at a ward or outpatient clinic, depending on whether the patient is hospitalized or policlinic.

Inclusion and exclusion criteria are reconciled and QMG, MG-ADL, MG-QOL15, EQ5D are performed and somatic status is checked.

Note that QMG testing should be performed ≥12 hours after last dose of cholinesterase inhibitors.

To reduce the risk of allergic reactions, 1,000 mg paracetamol (Alvedon), 50 mg prednisone (Deltison) and 10 mg Cetirizine are administered at least 45 minutes before the infusion. Blood pressure, pulse and temp are checked before starting the infusion.

Important: Before starting the infusion, take a serum tube for exploratory immunological analysis.

The blood sample is sent to the sample management Karolinska University Hospital Solna, attach study-specific consultant referral.

Study drug is administered as an intravenous infusion (2 mg rituximab / ml, total 500 mg or placebo) with increasing infusion rate for a total of about 150 minutes by the nurse in charge of the infusion with the physician in charge of the infusion as support. See Appendix 3, Mabthera Infusion Monitoring.

Speed of Infusion

0-30 min	50ml/h
30-60	100ml/h
60-90 min	150ml/h
90 min -	200ml/h

In case of allergic reactions, the infusion is stopped temporarily and if necessary, 0.5 - 1 mg clemastine (Tavegyl) iv and / or 100 mg hydrocortisone (Solu-Cortef) can be administered intravenously. If the symptoms subside, the infusion can be restarted at the initial drip rate. In case of more severe reactions affecting systemic condition or with circulatory effects, the infusion should be stopped permanently.

The patient is monitored throughout the infusion and blood pressure, pulse and temperature are checked again after the end of the administration. The patient is then observed for another 60 minutes.

Important: before returning home, make sure the patient has:

- Current contact information
- Informed to contact new / aggravated symptoms urgently, no later than 48 hours.
- Received instructions on medication with Prednisolone schedule if it has been deemed indicated

The prednisolone schedule listed below may, if Prednisolone has not already been started on a purely clinical indication, be initiated immediately after the screening visit, or alternatively the day after administration of study drugs, if cortisone treatment is judged clinically indicated by the treating physician:

Starting dose 40 mg / day, with tapering of 5 mg / week until discontinuation.

For patients already on Prednisolone before screening, the pre-screening dose may be increased to 40 mg / day with subsequent tapering according to the above schedule.

To reduce the risk of study endpoints being affected by another MG-specific treatment, such treatment should be given after randomization in accordance with section 10.7, Permitted / non-permitted treatment at different times.

If the cortisone dose can not be reduced due to persistent or worsening clinical symptoms, you may first choose to increase the dose of Prednisolone and make a new plan for phasing out or, secondly, to give rescue treatment with IvIg or PLEX.

Immunosuppressive therapy (azathioprine, ciclosporin, MMF, methotrexate) can be started if indicated from 12 weeks after randomization. Pulse cures with cortisone should not be given after randomization. In cases where the study physician for medical reasons considers that the above treatments are insufficient or inappropriate, other treatment may also be considered, including rituximab. The patient will then be classified as a non-responder in the primary outcome measure and censored in the secondary outcome measures.

Protocoll nr: 2015-00887 Date: 2021-04-26 Version 7.0 (ENG)

7.0 (ENG) 16(42)

8.5 Evaluation, observation period (24 weeks)

After the single administration of study drug, the effect is followed up according to the following schedule:

- Telephone contact with the study nurse after 2 weeks (+/- 2 days): checking for side effects, verifying current medication and Prednisolone dose.
- Return visit after 4 weeks (+/- 2 days): checking for side effects, verifying current drugs and Prednisolone dose, QMG, MG-ADL, MG-QoL15, EQ5D and somatic status.

Note that QMG testing should be performed 12 hours after the last dose of cholinesterase inhibitors and preferably at the same time of day throughout all testing sessions.

- Telephone contact with a nurse after 8 weeks (+/- 4 days): checking for side effects, verifying current medication and Prednisolone dose.
- Telephone contact with a nurse after 12 weeks (+/- 4 days): checking for side effects, verifying current drugs and Prednisolone dose.
- Return visit after 16 weeks (+/- 21 days): checking for side effects, verifying current drugs and Prednisolone dose, QMG, MG-ADL, MG-QoL15, EQ5D and somatic status.

Note that QMG testing should be performed 12 hours after the last dose of cholinesterase inhibitors.

Important: a serum tube for exploratory immunological analyzes is taken and sent to the sample management Karolinska University Hospital Solna, attach study-specific consultant referral.

- Telephone contact with a nurse after 20 weeks (+/- 7 days): checking for side effects, verifying current drugs and Prednisolone dose.
- Return visit after 24 weeks (+/- 21 days): checking for side effects, verifying current drugs and Prednisolone dose, QMG, MG-ADL, MG-QoL15, EQ5D and somatic status.

Note that QMG testing should be performed 12 hours after the last ingestion of cholinesterase inhibitors.

Important: a serum tube for exploratory immunological analyzes is taken and sent to the sample management Karolinska University Hospital Solna, attach study-specific consultant referral.

At the centers that have a neurophysiology clinic at the hospital, a repetitive nerve stimulation will be performed in connection with the return visit or in close proximity to the visit, see section 11.6 Neurophysiology.

8.6 Follow up period (25-48 weeks)

After a 24-week evaluation phase, the study moves to an open-label follow-up phase, where restrictions on other MG-specific therapies, including rituximab, no longer exist.

To provide information on the possible effects of the study drug in the longer term, two follow-up return visits are included:

• Return visit after 36 weeks (+/- 21 days): checking for side effects, verifying current drugs and Prednisolone dose, QMG, MG-ADL, MG-QoL15, EQ5D and somatic status.

Note that QMG testing should be performed 12 hours after the last ingestion of cholinesterase inhibitors.

• Return visit after 48 weeks (+/- 21 days): checking for side effects, verifying current drugs and Prednisolone dose, QMG, MG-ADL, MG-QoL15, EQ5D and somatic status.

Note that QMG testing should be performed 12 hours after the last dose of cholinesterase inhibitors.

See Section 20, Appendix 1 for flow chart

8.7 Study end

The study ends when the last patient has completed the last follow-up.

The study may be terminated prematurely if it turns out that the treatment causes a large number of undesirable serious events or if patient recruitment cannot be fulfilled within a reasonable time limit.

Protocoll nr: 2015-00887 Date: 2021-04-26

Version 7.0 (ENG) 17(42)

Decisions on early termination of studies are made by the sponsor / coordinating investigator.

When the study is completed, the Ethical Review Board and the Medical Products Agency will be informed of this in accordance with set time limits.

Protocoll nr: 2015-00887 Date: 2021-04-26

Version 7.0 (ENG) 18(42)

9 Study participants

9.1 Inclusion criteria

- 1. Patients with oculobulbar, bulbar or generalized MG \geq 18 years of age and \leq 12 months after onset of generalized symptoms or neurophysiological detection of generalized disease.
- 2. The diagnosis of MG should be made by the following tests: Clinical neurological status with motor symptoms compatible with MG and ≥ 2 of the following:
 - a Positive serological test for anti-acetylcholine receptor antibodies (AChR),

and/or

b. For MG typical findings on neuro-physiological testing of neuromuscular transmission by single fiber electromyography (SFEMG) and / or repetitive nerve stimulation (RNS),

and/or

- c. Positive anticholinesterase test, e.g. edrophonium chloride test or improvement of MG symptoms with oral cholinesterase inhibitors at the discretion of the treating physician.
- 3. MGFA clinical classification class II to IV at screening.
- 4. Quantitative MG score ≥ 6 at screening
- 5. Women of childbearing potential must have a negative pregnancy test.
- 6. Patients must have given written informed consent.
- 7. Patients must be able and willing to follow all study procedures.

9.2 Exclusion criteria

- 1. Weakness affecting only ocular or periocular muscles (MGFA class I).
- 2. MG crisis at screening (MGFA class V).
- 3. Thymectomy already performed. To avoid difficulties in evaluating the effect of the study drug, thymectomy, in cases where it is deemed indicated, should be planned for the follow-up period, i.e. only after the first 24 weeks.
- 4. Strong suspicion of thymoma and where thymectomy according to the treating physician should be performed within 24 weeks.
- 5. Activecancer, unless adequately treated.
- 6. Pregnancy or breast-feeding.
- 7. Any ongoing acute or chronic viral or systemic bacterial infection including HIV, latent hepatitis B, which is clinically significant in the opinion of the study physician, and which has not been treated with appropriate antibiotic / antiviral drugs.
- 8. Severe heart failure (New York Heart Association Class IV) or severe uncontrolled heart disease
- 9. Previous use of immunosuppressive drugs including rituximab, azathioprine, ciclosporin and MMF. The use of Prednisolone at a dose of ≤40mg / d within 3 months and IVIG and PLEX 12 months from the screening date does not constitute an exclusion criterion. Please also note that this does not apply to treatment with immunosuppressive drugs / corticosteroids (excluding rituximab) for indications other than MG, provided that > 12 months have elapsed since the end of treatment.
- 10. Hypersensitivity to the active substance, to murine proteins or to any of the other excipients in the study medicinal product
- 11. Participation in any other clinical drug study or exposure to any other study drug, study product or study procedures within 30 days before screening.
- 12. Any medical condition which, in the opinion of the study physician, may interfere with the patient's participation in the study, poses any additional risk to the patient, or which complicates the assessment of the patients.

Protocoll nr: 2015-00887 Date: 2021-04-26

Version 7.0 (ENG) 19(42)

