- 7. Patients must be able and willing to follow all study procedures.

Exclusion criteria

Weakness affecting only ocular or periocular muscles (MGFA class I).

- 2. MG crisis at screening (MGFA class V)
- 3. Thymectomy already performed. To avoid difficulties in evaluating the effect of the study drug, thymectomy, in cases where it is deemed indicated, should be planned for the follow-up period, i.e. only after the first 24 weeks.
- 4. Strong suspicion of thymoma and where thymectomy according to the treating physician should be performed within 24 weeks.
- 5. Active cancer, unless adequately treated
- 6. Pregnancy or breast-feeding.
- 7. Any ongoing acute or chronic viral or systemic bacterial infection including HIV and latent hepatitis B, which is clinically significant in the opinion of the study physician, and which has not been treated with appropriate antibiotic / antiviral drugs.
- 8. Severe heart failure (New York Heart Association Class IV) or severe uncontrolled heart disease
- 9. Previous use of immunosuppressive drugs including rituximab, azathioprine, ciclosporin and MMF. The use of Prednisolone at a dose of ≤40mg / d within 3 months and IVIG and PLEX 12 months from the screening date does not constitute an exclusion criterion. Note that this does not apply to treatment with immunosuppressive drugs / corticosteroids (excluding rituximab) for indications other than MG, provided that> 12 months have elapsed since the end of treatment.
- 10. Hypersensitivity to the active substance, to murine proteins or to any of the other excipients in the study medicinal product11. Participation in any other clinical drug
- study or exposure to any other study drug,

study product or study procedures within 30 days before screening.

12. Any medical condition which, in the opinion of the study physician, may interfere with the patient's participation in the study, poses any additional risk to the patient, or which complicates the assessment of the patients.

13. Vaccination within 4 weeks before inclusion

TIDSPLAN

Study period: Q4 2016 – Q1 2021

Recruitment period: Q4 2016 – Q1 2020

Protocoll nr: 2015-00887

Date: 2021-04-26

Version 7.0 (ENG)

2 Abbreviations

Förkortning	Förklaring
AE	Adverse Event
APL	Apotek Produktion & Laboratorier AB
CMM	Center for Molecular Medicine
DSUR	Development Safety Update Report
EQ5D	EuroQol 5-dimensions
GCP	Good Clinical Practice
ICH	International Conference on Harmonisation
IV	Intravenous

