8.2 Screening period

If the patient agrees to participate in the study, the following examinations are performed:

- Review of medical history and current medication
- Somatic status: including general condition (blood pressure, heart rate, body temperature), age, sex, height, weight and disease activity.
- Evaluation of muscle strength, QMG. If the patient has <6 in QMG, the evaluation must be repeated after at least 6 hours since last dose of cholinesterase inhibitors

Repetitive neurophysiology, RNS, for study subjects with a neurophysiology clinic in the hospital. See section 11.6, Neurophysiology

- Questionnaire regarding quality of life, EQ5D and MG-QoL15
- Ability to perform daily activities, MG-ADL.
- Blood tests: CBC incl. differential, Na, K, Creatinine, Asat, Alat, CRP, Glucose, hepatitis B screening, total IgG.
- Pregnancy test if the patient is a woman of childbearing age.

All women of childbearing potential are instructed to use effective contraception throughout the study after receiving the study drug. One of the following counts as an effective contraceptive:

- * Combined hormonal contraceptives (estrogen and progestin) that inhibit ovulation
- -oral, intravaginal, or transdermal
- * Progesterone -hormonal contraceptives that inhibit ovulation
- -oral, injectable, or implantable
- * Spiral
- * Bilateral fallopian tube occlusion
- * Vasectomized partner
- * Sexual abstinence, to refrain from heterosexual intercourse throughout the study.

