11.1 Blood samples

Blood samples for analysis of CBC including diff., Na, K, Creatinine, Asat, Alat, CRP, Glucose, hepatitis B screening and total IgG are taken at screening and analyzed at the local laboratory at each hospital.

Blood samples for analysis of drug antibodies and markers of disease activity, such as acetylcholine receptor antibodies, are taken in the study for evaluation of tertiary issue / exploratory analyzes in the study.

Analysis of autoantibodies is performed at Clinical Immunology / Transfusion Medicine, Karolinska University Laboratory after completion of the study.

Antibody antibodies and samples for exploratory analyzes will be sent to the Center for Molecular Medicine (CMM) at Karolinska Institutet (KI).

In total, a blood volume of about 50 ml is drawn from the patient during the study.

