¹Previous and current diseases, concomitant medications, blood pressure, heart rate, body temperature, age, sex, height, weight and disease activity. ²To be updated at all visits. ³ Haematology including differential count, electrolytes, creatinine, liver enzymes C-reactive protein, glucose, hepatitis B screening, total immunoglobulin G levels. ⁴ Fertile women. ⁵ Optional. No cholinesterase inhibitors within 12 hours before examination. ⁶ Myasthenia Gravis-Quality of Life. ⁷ Myasthenia Gravis-Activities of Daily Living. ⁸ Serum sample to be collected before administration of study drug.

Protocoll nr: 2015-00887 Date: 2021-04-26

Version 7.0 (ENG) 32(42)

⁹1 000 mg paracetamol, 50 mg prednisolone and 10 mg Cetirizine ≥ 45 min before administration of study drug. ¹⁰ Heart rate, blood pressure and body temperature to be recorded before and after administration of study drug. ¹¹ At or close to visit

21 Annex 2, MGFA classification

MGFA clinical classification

Class I: Any ocular muscle weakness; may have weakness of eye closure. Strength of all the other muscles is normal.

Class II: Mild weakness affecting muscles other than ocular muscles; may also have ocular muscle weakness of any severity.

IIa. Predominantly affecting limb, axial muscles, or both. May also have lesser involvement of oropharyngeal muscles.

IIb. Predominantly affecting oropharyngeal, respiratory muscles, or both. May also have lesser or equal involvement of limb, axial muscles, or both.

Class III: Moderate weakness affecting muscles other than ocular muscles; may also have ocular muscle weakness of any severity.

IIIa. Predominantly affecting limb, axial muscles, or both. May also have lesser involvement of oropharyngeal muscles.

IIIb. Predominantly affecting oropharyngeal, respiratory muscles, or both. May also have lesser or equal involvement of limb, axial muscles, or both.

Class IV: Severe weakness affecting muscles other than ocular muscles; may also have ocular muscle weakness of any severity.

IVa. Predominantly affecting limb, axial muscles, or both. May also have lesser involvement of oropharyngeal muscles.

IVb. Predominantly affecting oropharyngeal, respiratory muscles, or both. May also have lesser or equal involvement of limb, axial muscles, or both.

Class V: Defined as intubation, with or without mechanical ventilation, except when employed during routine postoperative management. The use of a feeding tube without intubation places the patient in class IVb.

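### Criterion 7 does not bar dosing in untreated latent hepatitis B that the study physician judges not clinically significant; other safeguards narrow this gap but do not close it

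*Combined protocol and SAP*

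**What the plan says.** **The exclusion rule.** Criterion 7 in section 9.2 concerns ongoing acute or chronic infections, "including HIV, latent hepatitis B, which is clinically significant in the opinion of the study physician, and which has not been treated" with appropriate antibiotic or antiviral drugs. The Summary (section 1) carries the same rule with slightly different punctuation: "including HIV and latent hepatitis B, which is clinically significant in the opinion of the study physician, and which has not been treated".

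**The screening.** Hepatitis B testing is on all three lists of screening tests:
- section 8.2: "Blood tests: CBC incl. differential, Na, K, Creatinine, Asat, Alat, CRP, Glucose, hepatitis B screening, total IgG";
- section 11.1: "hepatitis B screening and total IgG are taken at screening and analyzed at the local laboratory at each hospital";
- Annex 1, third footnote: "glucose, hepatitis B screening, total immunoglobulin G levels".

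None of these limits the test to a subgroup. Section 8.3 has randomization and drug ordering follow once the eligibility criteria are met.

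**The risk.** Section 15.3 states that rituximab raises the risk that some chronic infections get worse, and gives hepatitis B as the example.

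**The other safeguards.** Criterion 12 excludes any medical condition that, in the study physician's opinion, "poses any additional risk to the patient, or which complicates the assessment of the patients". Section 9.3 says the examiner *may* stop participation before dosing if new information suggests a risk with rituximab, with active hepatitis B among the examples. Section 8.4 has the eligibility criteria checked again on the day of dosing.

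**A firmer form in the same list.** Criterion 5 reads "Active cancer, unless adequately treated", with no condition about the physician's view of significance.

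**The concern.** The protocol identifies a hazard and orders a test for it in everyone. The rule that acts on the result then depends on an individual physician's view of whether a latent infection matters. Section 8.1 expects 10 to 15 centres, so the same positive result could lead to dosing at one and exclusion at another, with both following criterion 7.

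The entry decision carries most of the protection. Section 11.1 places liver enzymes and hepatitis B tests at screening only, and section 8.5 describes the week 16 and week 24 samples as serum for exploratory work. I found no scheduled liver or hepatitis B test after dosing. Section 12.5 also leaves events attributed to previously known diseases out of the adverse event record. A non-serious flare of a known infection might therefore not appear in the adverse event tables; serious events are still reported.

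What is at stake is patient safety: who may be dosed, and whether readers can see how positive screens were handled.

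**Working it through.** The documents give no figure to reproduce. The check reads criterion 7 as a rule, then asks whether any other text covers the case it leaves out.

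**Step 1: criterion 7 as a rule.** As written, in both 9.2 and the Summary, a patient is excluded if the infection is judged significant AND is untreated. With the opinion condition removed for hepatitis B, a patient is excluded if it is untreated. Antiviral prophylaxis counts here as treatment.

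| Latent hepatitis B | Excluded by criterion 7 now | Excluded without the opinion condition |
|---|---|---|
| judged significant, untreated | yes | yes |
| judged significant, treated | no | no |
| judged not significant, untreated | **no** | **yes** |
| judged not significant, treated | no | no |

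Exactly one row changes. The table locates the gap. It is not an effect size, because the four rows are not equally likely and the documents give no counts.

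**Step 2: is the result known in time?** Testing is part of screening (8.2, 11.1, Annex 1), and 8.3 makes randomization conditional on the criteria being met. Section 9.3 does foresee hepatitis B being detected between inclusion and dosing. In either case the protocol treats the result as something that can be acted on before the infusion.

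**Step 3: does other text close the gap?**

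| Provision | Could it stop dosing in the third row? | Does it have to? |
|---|---|---|
| Criterion 12 | Yes; its threshold is any additional risk | No; it rests on the physician's opinion |
| Section 9.3 | Yes; its trigger is broad and active hepatitis B is only an example | No; the examiner *may* act |
| Section 8.4 recheck | Only through the same criteria | Adds no new rule |
| Section 15.3 | It warns of the risk | It sets no eligibility rule |

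No text requires exclusion, treatment or prophylaxis for this patient.

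**Step 4: how many records are involved?** The Summary gives a study size of 47. Under 1:1 allocation, 47 / 2 = 23.5, so about 24 patients on rituximab. Placebo patients matter too: section 8.6 lifts the restriction on rituximab after week 24, and section 8.4 allows it earlier in exceptional cases.

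**Step 5: is dosing still going on?** The Summary states "Recruitment period: Q4 2016 – Q1 2020" and a study period ending in Q1 2021. This version is dated 2021-04-26. Study drug is given once, at baseline, so on these dates dosing appears complete.

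**The case against.** **Criterion 12 is a real barrier.** Its threshold is lower than clinical significance, and 15.3 tells every investigator that rituximab can worsen hepatitis B. To dose the patient in question, a physician would have to see the positive result, call it not significant under criterion 7, and also find no additional risk under criterion 12. This stands as a reason to expect few such cases. It does not supply an obligation, because both steps are the same person's opinion.

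**Section 9.3 reaches further than active infection.** Also correct: its trigger is any new information suggesting a risk, so a latent result could qualify. It remains permissive.

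**The text is a translation.** Naming HIV and latent hepatitis B might have been meant as a list of infections that always count. That is possible, but both copies attach the same two joined conditions to the named infections. If automatic exclusion was meant, the sentence needs rewording anyway.

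**Criterion 5 also involves judgement.** Whether treatment is adequate is a clinical decision, and the proposed wording keeps some of that discretion. What it removes is the discretion over whether an untreated infection needs any action.

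**Nothing is left to protect if dosing is over.** This carries weight. On the protocol's dates, rewording would help only a patient still to be dosed; otherwise the remedy reduces to reporting.

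**Stronger readings a reader might infer.** One is that patients with untreated latent hepatitis B were dosed or harmed. The documents report no positive screen and no such event. Another is that the protocol has no safeguard for these patients. Criterion 12, section 9.3 and the recheck in 8.4 show otherwise. A third is that leaving the screening markers unnamed is itself a fault; it is only missing detail.

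**Conclusion.** The point holds as a gap in a safety rule. Criterion 7 does not bar dosing in one identifiable situation, untreated latent hepatitis B judged not clinically significant, and no other provision obliges anyone to exclude or treat that patient. The surrounding provisions make such dosing less likely without ruling it out.

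Its size is one combination out of four in the rule, with an unknown number of patients. No frequency of wrongful dosing is claimed, and there is no effect on power or the primary analysis.

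The conclusion rests on reading the two conditions in criterion 7 as joint, which both copies support, and on the risk statement in 15.3. The documents do not quantify that risk for latent infection. That dosing is complete is inferred from the dates and is not stated outright. The change is worth making at moderate priority if anyone is still to be dosed; otherwise the reporting step is what remains.

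**What to change.** **If any patient is still to be dosed.** In section 9.2 and the Summary, take hepatitis B out of the opinion condition in criterion 7, following the form of criterion 5. A positive hepatitis B screen, active or latent, should bar dosing unless appropriate antiviral treatment, including prophylaxis, is given. In section 9.3, make this case mandatory: such a patient without antiviral cover must not receive study drug. The cost is a protocol amendment and a rare extra screen failure or antiviral course. Whether prophylaxis is suitable in this setting is for the clinical team to settle, since the documents do not discuss it.

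**If dosing is complete, as the dates suggest.** Review the hepatitis B screening results on file for the 47 patients. Report by arm how many were positive, whether those patients were dosed, and whether they had antiviral cover. The cost is a check of existing laboratory results and a short paragraph in the study report.

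Neither route needs a new test on patients. Stating in sections 8.2 and 11.1 which markers make up the screen, and which results count as positive, would help but is optional.
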